#### **3.5.3 Combined treatment and smoking**

All combined medications and treatments (including start/stop dates and indications) must be documented in the patient's original data as well as in the appropriate section of the CRF.

All patients taking combined drugs metabolized via CYP3A4 should be closely monitored for possible adverse effects of these drugs.

Smoking affects the pharmacokinetics of icotinib, and the smoking status, including the number and duration of cigarettes smoked per day, should be recorded during treatment. All patients are advised to quit smoking during treatment.

### **3.5.4 Concomitant medication**

#### **3.5.4.1 Drugs not allowed to be used**

- Bevacizumab and any drug that targets VEGF, VEGFR or EGFR (including registered or investigational drugs).
- Any other anti-cancer drug is not allowed except for study-specified icotinib, including investigational drugs (e.g., investigational antibiotics, antiemetics, etc.) and herbal medicines with anti-tumor indications.

#### **3.5.4.2 Permissible drugs**

- Non-anti-cancer herbal medicines or acupuncture, vitamins/trace elements are also allowed without affecting the study endpoints observed and are under the control of the Investigator.
- Patients may receive palliative treatment and supportive treatment for their pre-existing disease.

### **3.5.5 Treatment compliance**

The dose and date of administration of icotinib taken for each course of therapy for each patient should be documented in the CRF. Reasons for delayed administration, medication reduction, or missed doses should also be documented in the CRF.

Patient compliance with treatment and regimen includes voluntary compliance with all aspects of the regimen, including compliance with therapeutic agents, compliance with all blood collections required for safety assessment, and compliance with regular follow-up visits. Patients who do not take their medications on time, or who do not cooperate with tests, or who do not return to the study on time may be excluded

from the study based on the assessment of the principal investigator. Patients who discontinue icotinib due to unimprovable adverse reactions that do not resolve even with optimal symptomatic and supportive therapy may be withdrawn from the study if the duration of discontinuation is longer than 2 weeks, after discussion with and consent from the principal investigator.

### **3.6 Study endpoints**

The primary efficacy endpoint in this study is 3-year disease-free survival (DFS).

Secondary endpoints include disease-free survival (DFS), central nervous system (CNS)-related DFS, overall survival (OS), safety, and tolerability.

Exploratory analysis: to evaluate the efficacy of adjuvant icotinib for patients with completely resected stage IB NSCLC based on the AJCC 7th and 8th edition of staging.

To evaluate the efficacy of adjuvant icotinib for patients with completely resected stage IB NSCLC based on sensitive EGFR mutation and all EGFR mutations (including atypical EGFR mutations).

#### **3.6.1 Efficacy endpoints**

**Three-year Disease-Free Survival (DFS)** is defined as the proportion of patients who were disease free at 3 years.

**Disease-free survival (DFS)** is defined as the time between the date of randomization and the first confirmation of disease recurrence or death from any cause (whichever occurred first).

**Central nervous system (CNS)-related DFS** is defined as the time from randomization to CNS recurrence or death, whichever occurred first.

**Overall survival (OS)** is defined as the time between randomization and death from any cause. The 1-year overall survival is defined as the probability that the patient is alive for 1 year from the date of randomization. The 2-year overall survival is defined as the probability that the patient is alive for 2 years from the date of randomization. The 5-year overall survival is defined as the probability that the patient is alive for 5 years from the date of randomization.

The time that patients who are alive as of the date of analysis and are free of disease recurrence have

their last imaging evaluation is taken as the cutoff time.

### **3.6.2 Safety indicators**

All patients who have received at least one study drug treatment will serve as a valid population for safety analysis. Physical examination findings, vital signs, adverse events and abnormal laboratory test results of the patients will be summarized. Adverse events should be reported and graded according to the NCI Common Terminology Criteria for Adverse Events (CTCAE) Version 4.0.

## **3.7 Research process (see Table 1 for flow chart)**

### **3.7.1 Screening period**

- Sign an informed consent prior to any study-related operations.
- Acquire demographic information, and complete medical, surgical and smoking histories.
- Record/confirm the TNM stage of the primary tumor at the time of diagnosis.
- Evaluate tumor at chest-enhanced CT scan, upper abdomen-enhanced CT.
- Perform cranial enhanced MRI. Bone scan is performed only in patients with clinical symptoms.  
All examinations may be replaced by PET/CT.
- Take tumor tissue specimen and perform EGFR detection.
- Confirm that the subject meets the inclusion/exclusion criteria as specified in the study protocol.
- Perform physical examination: heart rate, blood pressure, respiratory rate, body temperature, height, weight and ECOG physical status scoring.
- Document all concomitant diseases and combined medications and their indications.
- Carry out routine blood tests: hemoglobin, HCT (hematokrit), platelet count, white blood cell count, and neutrophils.
- Perform blood biochemical tests: including blood glucose, calcium, phosphorus, sodium, potassium, chloride, creatinine, blood urea nitrogen (BUN), total protein, albumin, ALT, AST, alkaline phosphatase, total bilirubin, etc.

- Carry out a 12-lead electrocardiogram (ECG) examination at baseline stage, and check and sign by The Investigator.
- Perform urine pregnancy test on all female patients of childbearing age. Postmenopausal women who have been menopausal for at least 2 years and women who have undergone sterilization are not required to have the urine pregnancy test.
- Carry out routine urine tests: pH value, urine sugar, urine protein, ketone bodies, occult blood, urine bilirubin, red blood cells, and white blood cells.
- Perform HIV antibody tests.
- Perform pulmonary function tests.
- Perform tumor marker screening; collect biomarker blood sample specimen.
- Adverse events: signs and symptoms that exist prior to enrollment (prior to signing informed consent) and persist at enrollment should be documented per medical history. Any signs and symptoms that develop or worsen after enrollment (even before drug therapy) should be recorded as adverse events according to NCI-CTCAE Version 4.0.
- Distribute study drugs.

### 3.7.2 Visits

**Efficacy evaluation visits and subsequent visits (every 90 days  $\pm$ 7 days for the first 6 months and every 180 days  $\pm$ 7 days until 5 years)**

- Perform physical examinations (heart rate, blood pressure, respiratory rate, temperature, body weight and ECOG physical status scoring).
- Perform laboratory tests (hematology/blood biochemistry/urinary routine); perform ECG/pregnancy test.
- Collect biomarker samples (optional): take 10 ml of whole blood for molecular marker screening before treatment.
- Carry out tumor evaluation: it must include chest enhanced CT and upper abdomen enhanced CT. The follow-up period during treatment is every 3 months with an interval of +/- 7 days, covering the

chest and upper abdomen. All imaging tests can be replaced by PET/CT. Cranial MRI was scheduled every 12 months. Bone scan will be performed only when clinically indicated.

- Document adverse events and combined medications since the last visit.
- Make an appointment for a next visit.

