Duration of study	It is planned to enroll 128 patients based on about 6 patients enrolled each month; and the time for enrollment is about 24 months; the minimum survival follow-up period is 3 years, and the total study period will last about 60 months.
Study Drug Dosage/Route of Administration/Regimen	
Group A (icotinib group): Patients start to receive oral icotinib 125 mg, tid, for 12 months after R0 resection of NSCLC, or discontinue treatment due to tumor recurrence or intolerance.
 
Group B (control group) Patients are followed up after R0 resection of NSCLC.

Study Procedure	
After patients have signed the informed consent forms (ICFs) and meet the inclusion and exclusion criteria, they will be randomly assigned to the icotinib group and the control group.
 
Patients need to be evaluated. The patients receive the visits once every 3 months during the dosing period, and once every 6 months for the survival follow-up until the disease recurrence or death.
 
The Investigator shall contact the patient, the patient's family, or the patient's current physician by phone at least once every 3 months after recurrence, to collect the long-term follow-up information on survival. Any patient who withdraws from study treatment for reasons other than recurrence (except patient's withdrawal of informed consent, loss to follow-up, death) should continue to receive the objective tumor evaluation every 6 months to collect the information on recurrence.

Safety	All patients who have received at least one treatment with study drug will be included as the effective population for safety analysis. The patient's physical examination results, vital signs, adverse events, and abnormal laboratory test results will be summarized. Adverse events should be reported and graded according to the NCI Common Terminology Criteria for Adverse Events (CTCAE) version 4.0.
Statistical Analysis	The sample size is 128 for the following considerations: based on previous studies, the 3-year DFS for stage IB NSCLC is about 60%, the hazard ratio (HR) is 0.5, the test power ( $1 - \beta$ ) is 80%, and the test level ( $\alpha$ ) is two-sided 10%; enrollment period of 24 months, and total study period of 60 months.

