## Summary

[figure not shown]

Table 1 Study Flow Chart

Study period	Screening	Randomization				Follow-up after recurrence M C=3 months	
		Group A (icotinib group)		Group B (control group)			
		C1-C2 C=3 months	5-year survival follow-up C=6 months Survival follow-up after 5 years C= 12 months	C1-C2 C=3 months	5-year survival follow-up C=6 months Survival follow-up after 5 years C= 12 months		
	Day -42 to Day -0	Day -7 to Day 0	Day 1		Day 1		
Screening management	Informed Consent/Demographics/Medical History A	×					
	Inclusion/exclusion criteria review		×				
	Urine pregnancy test B		×				
Safety data	ECG C	×					
	ECOG Performance Status/Height/Weight/Vital Signs D		×	×	×	×	
	Adverse event E	×		×	×	×	
	Subsequent treatment and survival					×	
	Medication record F			×	×		
Preoperative and follow-up examinations	Physical examination	×	×	×	×	×	
	Enhanced chest CT + enhanced upper abdominal CT G	×		× G	× G	× G	
	Assessment of other sites H	×					
	Clinical Biochemistry/Hematology/Urine Routine I	×		×	×	×	
	FACT-L and LCS Questionnaire J		×	×	×	×	
	Tissue specimens or sections for biomarker studies K	×					
	Blood specimens for biomarkers (optional) L	×		×	×	×	
	Pulmonary function/HIV antibody/tumor markers	×					

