- F. Data on combined medication are collected, including drug dose, route of administration, schedule of administration, start date, indications, end date, and reason for end, and must be recorded from randomized use of the study drug until 1 month after drug discontinuation. The treating physician receives this information from the patient's hospital efficacy follow-up visits every 30 days. By knowing the routinely prescribed medications, the treating physician evaluates whether clinically significant improvement in pulmonary symptoms is likely to result from changes in the patient's combined medication over the past 30 days.
- G. Pre-operative and evaluation of tumor recurrence imaging must include chest-enhanced CT, upper abdomen-enhanced CT. Tumor evaluation during the follow-up period is performed every 6 months with a window phase of +/- 7 days, covering the chest and upper abdomen. All imaging studies could be replaced by PET/CT.
- H. Brain MRI was scheduled every 12 months. Bone scans and other examinations are "recommended" during the screening period to rule out distant metastases. Usually hospitals will routinely examine them. Subsequently, bone scans and other examinations will be done with clinical indications.
- I. Hematology (hemoglobin, erythrocyte pressure, platelets, leukocytes, absolute neutrophil values, absolute lymphocyte values) / blood biochemistry (glucose, calcium, phosphorus, sodium, potassium, chloride, creatinine, blood urea nitrogen, total protein, albumin, ALT, AST, alkaline phosphatase, total bilirubin, etc.) / urinalysis (urine specific gravity, pH value, urine glucose, urine protein and occult blood) should be completed within 7 days before the first dose, at each follow-up visit and 7 days before and after withdrawal from the study, and when clinically indicated, with specific additional frequency as appropriate.
- J. The patient self-assessment outcome questionnaire FACT-L and LCS Version 4 should be completed at each efficacy evaluation.
- K. Tissue specimens will be taken during surgery.
- L. For each efficacy visit cycle, 10 ml of whole blood is taken for biomarker analysis prior to treatment, and the blood sample is processed and transported for storage.
- M. The time window for follow-up after recurrence is every 90 days  $\pm$  7 days.

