efficacy than first-line chemotherapy regimens in the treatment of patients with EGFR mutations at stage IIIB-IV, and therefore has become the first-line treatment standard for this population. Postoperative adjuvant targeted therapy for NSCLC is currently a hot topic of research, for example, a phase III randomized clinical trial (BR.19 study) investigated the efficacy of postoperative adjuvant gefitinib therapy for NSCLC at stage IB-IIIA. The patients were randomized to receive postoperative gefitinib or placebo for 2 years, and 503 patients were enrolled between 2002 and 2005 with median treatment duration of 4.8 months. The results showed a DFS of 4.2 years and an OS of 5.1 years in the gefitinib-treated group, indicating that the lifetime of the patients was not significantly prolonged when compared with that of the placebo group, but patients with EGFR mutations were not selected for this trial. Another RADIANT phase-III clinical study included patients with positive EGFR at stage I-IIIA (IHC or FISH) with postoperative erlotinib for 2 years to evaluate the role of erlotinib in adjuvant therapy, with a placebo control group, and the population enrolled in this study was also not selected on the basis of EGFR mutations. In 2011, MSKCC retrospectively analyzed 167 lung adenocarcinoma patients with stage I-III EGFR mutations from 2002-2008, 56 of whom were treated with targeted therapy in the perioperative period, and a survival analysis comparison with patients without targeted therapy showed that the former had a higher 2-year DFS than that of the latter (89% vs 70%), and despite that the p-value (0.06) was not statistically significantly different, the adjuvant targeted therapy group showed a trend of benefit. A phase-II clinical study was reported in the SELECT study at the ASCO meeting in 2012, that is, patients with stage IA-IIIA mutant lung cancer were treated with postoperative erlotinib for 2 years following standard adjuvant chemotherapy or adjuvant radiotherapy. This study enrolled a total of 36 patients, of which 11 patients were on the drug for less than 2 years. After a median follow-up period of 2.5 years, the 2-year DFS rate was as high as 94%.

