### **3.5 Treatment plan**

#### **3.5.1 Treatment schedule**

The enrolled patients are randomized to a group treated with icotinib for 12 months or a control group. Patients of the icotinib group are administrated with 125 mg of icotinib orally, tid, for 12 consecutive months after surgery, or discontinued due to disease recurrence or intolerable toxic reactions, and the control group is merely followed up.

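### Protocol 3.7.2 gives two year-1 schedules, one tied to treatment, so scan timing can depend on arm and treatment status; the effect is small and one common schedule would remove it

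*Protocol*

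**What the plan says.** Two rules for year 1 stand side by side in Protocol 3.7.2.

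- The heading sets visits every 90 days "for the first 6 months and every 180 days" thereafter, up to 5 years. Table 1 agrees: its column header for both groups is "C1-C2 C=3 months", that is two 3-month cycles, followed by 6-month cycles.
- The tumour-evaluation bullet under that heading says "The follow-up period during treatment is every 3 months with an interval of +/- 7 days". The synopsis words visits in the same way: "The patients receive the visits once every 3 months during the dosing period, and once every 6 months for the survival follow-up".

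Dosing lasts 12 months and exists in one arm only; Protocol 3.5.1 says "and the control group is merely followed up". Footnote G to Table 1 adds "Tumor evaluation during the follow-up period is performed every 6 months with a window phase of +/- 7 days", without saying when the follow-up period begins.

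For patients who stop study treatment for reasons other than recurrence, the synopsis says they "should continue to receive the objective tumor evaluation every 6 months to collect the information on recurrence". It gives no start point for the six months. The discontinuation visit in 3.7.2 has a date, but its list of assessments includes no imaging. The SAP contains no visit or imaging schedule.

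**The concern.** A site cannot follow both rules at month 9. If it follows the treatment-based wording, icotinib patients are scanned at day 270 and controls are not. If the 6-monthly rule after early stopping is counted from the stop, those patients leave the common calendar, and only icotinib patients can stop treatment.

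Recurrence is dated when it is found, so unequal scan times produce unequal event times even when the true recurrence times are the same. The protection against this should be strict here: the trial is open-label (SAP 3.3), and the DFS analysis uses the investigator's assessment, although an independent committee also reviews the images (Protocol 9). The primary endpoint could be affected if the last scan before the 3-year cut fell at different times in the two arms. The secondary DFS comparison could be affected by any difference in dating.

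**Working it through.** **Inputs from the documents.** Control 3-year DFS 60%, HR 0.5, 128 patients (64 per arm), 2-year accrual and 3-year follow-up (SAP 5); 12 months of dosing (Protocol 3.1); a year is 365 days (SAP 11), so the 3-year cut is day 1095. The plan states no figure on this point, so there is none to reproduce.

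**Step 1: lay out the two calendars.**

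| Source | Scheduled days to year 3 |
|---|---|
| 3.7.2 heading, Table 1 | 90, 180, 360, 540, 720, 900, 1080 |
| 3.7.2 imaging bullet; synopsis (visits) | 90, 180, 270, 360, 540, 720, 900, 1080 |

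The only difference is day 270.

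**Step 2: primary endpoint on either calendar.** Take exponential DFS, S(t) = 0.6^(HR × t/1095), with each recurrence dated at the next scheduled scan. The last scan before day 1095 is day 1080 on both calendars, so the observed 3-year DFS is S(1080):

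- control: 0.6^(1080/1095) = 60.4%
- icotinib: 0.6^(0.5 × 1080/1095) = 77.7%

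The extra scan changes neither value.

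**Step 3: secondary DFS if only icotinib has day 270.** The share of the icotinib arm recurring between days 180 and 270 is S(180) − S(270) = 2.0%. Those events are dated 90 days earlier than they would be at day 360. In 6,000 simulated paired trials (5% dropout by 3 years, full attendance, censoring at the last scan as in Protocol 3.6.1), the log-HR moved by 0.0025. The HR went from 0.493 to 0.494, and log-rank power at two-sided 10% from 75.6% to 75.0%. A separate simulation of 3,000 trials gave 76.2% and 75.6%. If control were also denied day 90 and scanned only at days 180 and 360, the log-HR shift was 0.0050 and the HR about 0.496. That needs footnote G to be applied to the first 6 months of the control arm alone. Both shifts are against icotinib.

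**Step 4: scans counted from an early stop (a possible reading, not a stated rule).** Let the stop day d be uniform over days 1 to 359, with scans every 180 days from d. The last scan at or before day 1095 then averages about day 1005, instead of day 1080. For example, a stop on day 120 gives 120 + 5 × 180 = 1020. Averaging S(last scan) − S(1080) over d gives, per early stopper:

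- HR 0.5: +1.37 points (range −0.3 to +3.0 by stop day)
- no true effect: +2.16 points

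The documents give no early-stop rate for this regimen, so I assume 20%. The whole-arm shift is then 0.20 × 1.37 = 0.27 points, or 0.20 × 2.16 = 0.43 points with no true effect. Simulation gave 0.19 and 0.29 with censoring at the last scan, and 0.27 and 0.44 with censoring at last contact (SAP 12). At HR 0.5, shares of 5% and 30% give 0.07 and 0.41 points.

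For scale, the standard error of the 3-year difference with 60% in both arms is sqrt(2 × 0.6 × 0.4/64) = 8.66 points. A shift of 0.43 points is 0.05 standard errors. It raises false rejections in favour of icotinib on the 3-year Z test from 5.0% to 1 − Φ(1.645 − 0.05) = 5.5%, at two-sided 10%.

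**Direction of error.** All of these figures date every event at a scheduled scan. DFS also counts deaths, and Protocol 3.7.4 allows visits when clinically indicated, so the true shifts would be smaller.

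**The case against.** The strongest reply is that a common calendar was intended. Table 1 prints the same headers, with Day 1, for both groups, and section 3.7 refers the reader to Table 1. The synopsis sentence on the dosing period concerns visits, not imaging. The early-stop sentence speaks of continuing evaluation, which suggests staying on the existing calendar, and there is no scan at discontinuation from which a new count could begin. All of this stands. It shows the likely intention, but it does not remove the bullet in 3.7.2, which is an imaging rule and uses treatment as its time base.

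Three stronger readings are tempting and are not supported.

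- A reader might infer that the primary endpoint is tilted towards icotinib. That requires scans to restart at the stop date, which no section prescribes.
- A reader might infer frequent early stopping from the Background. In a cited erlotinib study of 36 patients, "of which 11 patients were on the drug for less than 2 years"; at a constant rate, 1 − sqrt(25/36) is about 17% by 12 months. In a cited gefitinib trial, median treatment was 4.8 months of a planned 2 years. These are other drugs on 2-year courses, and reasons for stopping are not given, so recurrence, which the synopsis rule excludes, may be among them. They do not establish a rate for 12 months of icotinib. The 20% above is only an illustration.
- A reader might infer a 180-day gap in laboratory safety monitoring while patients are on the drug. Footnote F refers to hospital visits every 30 days, and footnote I asks for laboratory tests at each follow-up visit and when clinically indicated, so such a gap is not established. Footnote F does not match any other schedule in the protocol, which is a reason to align it too.

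**Conclusion.** The point holds as a minor one. Protocol 3.7.2 states two incompatible year-1 schedules, one of them tied to treatment, and the synopsis leaves the interval after early stopping without an anchor. As written, this lets scan timing depend on arm and treatment status.

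The wording conflict is certain. Its numerical consequence is slight and rests on exponential DFS, full attendance and scan-dated events. On the day-270 difference alone the primary endpoint is unaffected and the secondary HR moves in the third decimal, against icotinib. A gain for icotinib on the primary endpoint, a few tenths of a point, arises only under the unstated re-anchoring and an assumed stopping share. Nothing here threatens the trial's conclusion. The reason to act is that an avoidable source of unequal ascertainment can be removed at almost no cost.

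**What to change.** State one imaging schedule, counted from randomisation, identical in both arms and kept after early discontinuation of icotinib. Either version serves:

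- days 90, 180 and 360, then every 180 days to year 5; or
- the same with day 270 added in both arms,

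each ±7 days. Align the synopsis (including the sentence on early stopping), Table 1, footnotes F and G and Protocol 3.7.2 to it. The first version costs only a protocol clarification; the second adds at most one scan per patient.
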